### 3.9.9.4.2 TNF $\alpha$ Related mRNA expression

TNF $\alpha$  related genetic expression of mRNA were found from the study by Smiljanovic et al. who did in vitro stimulation of whole blood with TNF $\alpha$  to study the mRNA expression of circulating macrophages. As well as other authors, noted in Table 5.

Only the genes upregulated by IL-6 and TNF $\alpha$  respectively will be included in the geometric and standardised scores for these genes (see above)

3.9.9.4.2.1 TNF $\alpha$	15 Genes (13 Unique)	
Abbreviation	Gene	Function  (according to Genecards.org)
ADAM17 	A Disintegrin And Metalloproteinase domain 17	Protein Coding gene. Diseases associated with ADAM17 include Inflammatory Skin And Bowel Disease, Neonatal, 1 and Neonatal Inflammatory Skin And Bowel Disease. Among its related pathways are Signaling by NOTCH1 and NOTCH2 Activation and Transmission of Signal to the Nucleus. Gene Ontology (GO) annotations related to this gene include SH3 domain binding and integrin binding. An important paralog of this gene is ADAM10.
ARNTL2 	Aryl Hydrocarbon Receptor Nuclear Translocator Like 2	Protein Coding gene. Diseases associated with ARNTL2 include Hepatorenal Syndrome and Acute Kidney Failure. Among its related pathways are Circadian rythm related genes and BMAL1-CLOCK,NPAS2 activates circadian gene expression. Gene Ontology (GO) annotations related to this gene include DNA-binding transcription factor activity and protein dimerization activity. An important paralog of this gene is ARNTL.
CASP3 	Caspase 3	Protein Coding gene. Diseases associated with CASP3 include Oropharynx Cancer and Ischemia. Among its related pathways are TNFR1 Pathway and ERK Signaling. Gene Ontology (GO) annotations related to this gene include peptidase activity and cysteine-type peptidase activity. An important paralog of this gene is CASP7.
CASP5 	Caspase 5	Protein Coding gene. Diseases associated with CASP5 include Cowpox and Familial Mediterranean Fever. Among its related pathways are TRAF Pathway and Apoptosis and Autophagy. Gene Ontology (GO) annotations related to this gene include cysteine-type endopeptidase activity and scaffold protein binding. An important paralog of this gene is CASP4.
CCR1 	C-C Motif Chemokine Receptor 1	Protein Coding gene. Diseases associated with CCR1 include Behcet Syndrome and Immune-Complex Glomerulonephritis. Among its related pathways are Innate Immune System and Chemokine Superfamily: Human/Mouse Ligand-Receptor Interactions. Gene Ontology (GO) annotations related to this gene include G protein-coupled receptor activity and chemokine receptor activity. An important paralog of this gene is CCR3.
CD22/ SIGLEC2 	Sialic Acid-Binding Ig-Like Lectin 2	Protein Coding gene. Diseases associated with CD22 include Refractory Hematologic Cancer and Hairy Cell Leukemia. Among its related pathways are Antigen activates B Cell Receptor (BCR) leading to generation of second messengers and Innate Immune System. Gene Ontology (GO) annotations related to this gene include carbohydrate binding. An important paralog of this gene is SIGLEC1.

GJA3 	Gap Junction Protein Alpha 3	Protein Coding gene. Diseases associated with GJA3 include Cataract 14, Multiple Types and Early-Onset Posterior Polar Cataract. Among its related pathways are Myometrial Relaxation and Contraction Pathways and Gap junction trafficking. Gene Ontology (GO) annotations related to this gene include gap junction channel activity. An important paralog of this gene is GJA8.
GPR35 	G Protein-Coupled Receptor 35	Protein Coding gene. Diseases associated with GPR35 include Cholangitis, Primary Sclerosing and Short-Rib Thoracic Dysplasia 10 With Or Without Polydactyly. Among its related pathways are Peptide ligand-binding receptors and Signaling by GPCR. Gene Ontology (GO) annotations related to this gene include G protein-coupled receptor activity. An important paralog of this gene is GPR55.
MAP3K7IP3/ TAB3 	Mitogen-Activated Protein Kinase Kinase Kinase 7 Interacting Protein /TGF-Beta Activated Kinase 1 (MAP3K7)	Protein Coding gene. Among its related pathways are Activated TLR4 signalling and MAP Kinase Signaling. An important paralog of this gene is TAB2.
MCP-1/CCL2 	Monocyte Chemotactic Protein 1 / C-C Motif Chemokine Ligand 2	Protein Coding gene. Diseases associated with CCL2 include Neural Tube Defects and Human Immunodeficiency Virus Type 11. Among its related pathways are p70S6K Signaling and A-beta Uptake and Degradation. Gene Ontology (GO) annotations related to this gene include protein kinase activity and heparin binding. An important paralog of this gene is CCL7.
PLAUR (downregulated) 	Plasminogen Activator, Urokinase Receptor	Protein Coding gene. Diseases associated with PLAUR include Cancer of the Ureter and Paroxysmal Nocturnal Hemoglobinuria. Among its related pathways are Post-translational modification-synthesis of GPI-anchored proteins and Transcription Receptor-mediated HIF regulation. Gene Ontology (GO) annotations related to this gene include signaling receptor binding. An important paralog of this gene is LYPD3.
PPAP2A / PLPP1 	Phospholipid Phosphatase 1	Protein Coding gene. Diseases associated with PLPP1 include Myxosarcoma. Among its related pathways are Androgen receptor signaling pathway and triacylglycerol biosynthesis. An important paralog of this gene is PLPP2.
PPP1CA 	Protein Phosphatase 1 Catalytic Subunit Alpha	Protein Coding gene. Diseases associated with PPP1CA include Venezuelan Equine Encephalitis and Encephalitis. Among its related pathways are Circadian rythm related genes and Development Ligand-independent activation of ESR1 and ESR2. Gene Ontology (GO) annotations related to this gene include hydrolase activity and phosphoprotein phosphatase activity. An important paralog of this gene is PPP1CC.
SPP1 	Secreted Phosphoprotein 1	Protein Coding gene. Diseases associated with SPP1 include Pediatric Systemic Lupus Erythematosus and Urolithiasis. Among its related pathways are Integrin cell surface interactions and Development Hedgehog and PTH signaling pathways in

		bone and cartilage development. Gene Ontology (GO) annotations related to this gene include cytokine activity and extracellular matrix binding.
SYNGR3 	Synaptogyrin 3	Protein Coding gene. Diseases associated with SYNGR3 include Deafness, Autosomal Recessive 74 and Deafness, Autosomal Recessive 86. Gene Ontology (GO) annotations related to this gene include protein N-terminus binding and SH2 domain binding. An important paralog of this gene is SYNGR1.

Table 5 Genes related to TNFa to be tested for mRNA expression

### 3.9.10 Urine Samples

Urine samples will be collected, and analyzed by dipstick at CFAS screening for hematuria, proteinuria, glucosuria, leukocyturia and nitrituria.

### 3.9.11 SLE disease activity measures

At baseline and follow-up, PROMs will be collected from questionnaires including Fatigue Severity Scale and VAS fatigue, VAS pain and Short Form (SF)-36 Health Survey.

Patients will be evaluated by a blinded study MD, using the SLEDAI-2K system (With the SELENA modifications), the SR-50, Q-SLAQ score, as well as VAS Physician of overall disease at both inclusion and follow-up.

### 3.9.12 Rb-PET Scan

A subgroup of patients, chosen from their Lupus Anticoagulant and Sjögren antibody status, up to 40, will undergo a serial rest–stress imaging on a Biograph mCT 128-slice scanner (Siemens Healthcare) using list-mode 3D acquisition after Rb infusion (Bracco Diagnostics). Low-dose CT (0.4 mSv; 120 kVp; effective tube current, 26 mA [11-mAs quality reference]; 3.3 seconds) will be performed for attenuation correction during normal breathing. Stress will be induced with adenosine infused at 140 µg/kg/min for 6 minutes, with acquisition starting 2.5 minutes later. Coronary artery calcium score (CACs) images and the quantitation of pericardial fat will be acquired from a non-contrast breath-hold CT at the first scan. Myocardial blood flow will be quantitated from dynamic rest and stress images with quantitative-gated nuclear imaging based on a single compartment Rb tracer kinetics model using syngo.MBF (Siemens Medical Solutions, Version VB15, Illinois, USA), and Corridor4DM v. 2015.0.0.44 (INVIA, LLC, Ann Arbor, USA). The myocardial flow reserve, which may be used to unveil microvascular disease in these patients will be calculated as myocardial blood flow at adenosine-induced maximal hyperaemia divided by resting myocardial blood flow. Based on left ventricular contours, ventricular volumes and ejection fraction will be determined.

### 3.9.13 Oral glucose tolerance test

A standard 2-hour 75 g OGTT will be performed with a serial of blood drawn at baseline, after 60 min and after 120 min. These samples will be analyzed for glucose, insulin, and c-peptide as per 3.9.7.4.

### **3.9.14 Lung function**

Standardised lung function testing will be performed in accordance with consensus guidelines at using equipment at CFAS. This encompasses dynamic spirometry, body plethysmography, and diffusing capacity. Based on summary equations, the expected values according to height, age and sex will be calculated.

### **3.9.15 Nailfold Capillaroscopy**

Peripheral capillaries will be assessed at baseline and follow-up by nailfold capillaroscopy, a technique routinely used in the clinic for patients with systemic scleroderma, SLE or dermatomyositis. This is a non-invasive examination where a clinician uses a capillaroscope, in essence a powerful digital microscope, to examine the peripheral capillaries of the subjects nailfolds.

### **3.9.16 Autonomic Nerve Function tests**

Using a handheld external device that measured the first lead of an ECG, participants will be instructed to stand up from supine position, do a controlled breathing exercise and then a Valsalva manoeuvre while measuring the RR interval.

### **3.9.17 Muscle biopsies**

Muscle biopsies will not be required for participation in the study and will be entirely optional.

After anesthetising the skin with up to 10ml Lidocaine 20mg/Noradrenalin5microgram/ml, approximately 100-200 mg of skeletal muscle tissue will be extracted from the quadriceps muscle under sterile conditions. The samples are then immediately frozen in liquid nitrogen and stored at -80°C until analysis.

Upon completion of the study, the samples will be analysed en bloc for fiber type, inflammatory markers, expression of multiple genes, including, but not limited to: NF-κB p65 DNA binding activity (ELISA), phosphorylated and total JNK, phosphorylated AMPK (p-AMPK) total AMPK (Western blotting), mRNA expression of genes as described in 3.9.9, as well as NF-κB binding activity (Western blotting).

### **3.9.18 Data analysis**

At least 10 participants in each intervention group and 10 participants in each control group, will be included to obtain a significance level of 0.05 with a power of 80% to observe an increase in VO2max of 1.14ml/kg/min with a SD of 2.15 in the control group and an increase in VO2max of 3.80ml/kg/min with a SD of 3.34 in the intervention group based on a previous publication. If we assume a drop-out rate of less than 30% with 15 participants in each group, we will have at least a power of 80% even with 30% drop-out. With 14 participants in each group, we will achieve a power of 90%.

Similar results were gained when examining the study by Boström et al. were the control group had an increase in VO2max of 1.7ml/kg/min with an SD of 1.3 and the intervention group had an increase of 3.2ml/kg/min with an SD of 1.2. A significance of 0.05 and a power of 80% requires 12 subjects in each group.

Since we hope to be able to part our groups into patients with higher IFNGS being the patients with M3.4 and M5.12 and we assume one third of our patients will be in this group, including 30 patients for intervention will give us 10 “high IFNGS intervention” patients in total for this power calculation.

Results will be analysed according to a pre-defined statistical analysis plan and initial modelling of the primary outcome will be based on Analysis of Covariance (ANCOVA) performed with change (post-measure minus pre-measure) as the dependent outcome, with a fixed factor for group (two levels) and applying the value at baseline as a covariate.

$$k = \frac{n_2}{n_1} = 1$$

$$n_1 = \frac{(\sigma_1^2 + \sigma_2^2/K)(z_{1-\alpha/2} + z_{1-\beta})^2}{\Delta^2}$$

$$n_1 = \frac{(2.15^2 + 2.15^2/1)(1.96 + 0.84)^2}{2.66^2}$$

$$n_1 = 10$$

$$n_2 = K * n_1 = 10$$

$\Delta = |\mu_2 - \mu_1|$  = absolute difference between two means  
 $\sigma_1, \sigma_2$  = variance of mean #1 and #2  
 $n_1$  = sample size for group #1  
 $n_2$  = sample size for group #2  
 $\alpha$  = probability of type I error (usually 0.05)  
 $\beta$  = probability of type II error (usually 0.2)  
 $z$  = critical Z value for a given  $\alpha$  or  $\beta$   
 $k$  = ratio of sample size for group #2 to group #1

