4 TRIAL DESIGN, DATA COLLECTION AND OUTCOMES ASSESSMENT

The study protocol, detailing the hypotheses, methods, recruitment and conduct of the study has been published in a non-peer reviewed openly accessible preprint database³⁵. In brief, the study is a randomized control trial, consisting of 2 arms, labeled exercise and control. As outlined in the publicly available protocol³⁵; initial sample size calculations were based on a t-test for changes in VO₂max. Assuming a between group difference in aerobic capacity change scores similar to the 1989 Robb-Nicholson study³⁶ (mean: 2.66, 95%CI [0.36, 4.96]); resulted in 10 completers needed in each group, if we assumed a median split of IFN-score we would require 40 completers for four groups (low IFN control, Low IFN exercise, High IFN control and high IFN exercise). We assumed as much as a 30% dropout; which required a sample size of 60 participants. After reaching 40 completers, recruitment ceased, and only further participants already enrolled for baseline examination were included, this resulted in 55 participants included in the study. These were then stratified for sex and randomly allocated 1:1 to exercise or control. At www.clinicaltrials.gov the study is identified by NCT05478018. Prior to commencement the scientific ethics committee of the capital region of Denmark approved to trial with identifier H-21039032. The trial primarily took place at Centre for Physical Activity on Rigshospitalet, [name]. Recruitment took place primarily at the center for vasculitis and spine diseases on Rigshospitalet in [name]. 82-Rb-Pet-CT scans were conducted at the department of clinical physiology at Rigshospitalet, [name].

[figure not shown]

Figure 1 - Graphical hypothesis

The exercise group underwent 12 weeks of thrice weekly 45 minute HIIT exercise sessions, with 4 intervals of 4 minutes of high intensity exercise, defined as a heart rate above 85% of the maximal heart rate interspersed with 3 minute active breaks of pedaling against light resistance (less than 20% wattmax).

As noted above the hypotheses were that these 12 weeks would improve aerobic capacity and fatigue in SLE patients, and that it would improve more in patients with lower IFNGS.

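### The 10 completers per group are 10.24 rounded down on normal quantiles; on the entered inputs (SD 2.15 in both arms) the t-test named in the SAP gives 74% power at 10, not 80%, and needs 12

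*Protocol*

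**What the plan says.** Protocol 3.9.18 sets the size "to obtain a significance level of 0.05 with a power of 80" per cent. From its first planning source it takes "an increase in VO 2 max of 1.14ml/kg/min with a SD of 2.15 in the control group" and "3.80ml/kg/min with a SD of 3.34 in the intervention group". The formula it prints contains "2.15^2 + 2.15^2/1)(1.96 + 0.84)^2" over 2.66 squared, and the result is given as 10 per group.

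On drop-out it states: "If we assume a drop-out rate of less than 30% with 15 participants in each group, we will have at least a power of 80" per cent. It also claims 90% power at 14 per group. For a second source (control 1.7, SD 1.3; intervention 3.2, SD 1.2) it states: "A significance of 0.05 and a power of 80% requires 12 subjects in each group". It describes the two sources as giving similar results and carries the 10 forward, as the expected number of high-IFNGS patients among 30 exercisers.

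SAP section 4 says that "initial sample size calculations were based on a t-test for changes in VO₂max", and that this "resulted in 10 completers needed in each group, if we assumed a median split of IFN-score we would require 40 completers for four groups". It enlarges the 40 to 60 for drop-out and reports that recruitment stopped once 40 completers were reached, with 55 participants included.

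**The concern.** A figure offered as giving at least 80% power should be rounded up, and the method behind it should match the test that is named. Here the result is rounded down, and the formula uses normal quantiles although the SAP names a t-test. At about 10 per group, the difference between the normal and t distributions costs several points of power.

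The figure had a practical role. It became the completer requirement per cell, was multiplied to 40, and 40 was the point at which recruitment stopped. A reader of the SAP would conclude that each exercise-versus-control comparison within an IFNGS half had 80% power.

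**Working it through.** **Inputs (protocol 3.9.18).** First source: difference 3.80 − 1.14 = 2.66; SD entered 2.15 in both arms; SDs stated 2.15 and 3.34. Second source: difference 3.2 − 1.7 = 1.5; SDs 1.3 and 1.2. Two-sided alpha 0.05, target power 80%, 1:1 allocation.

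**1. The plan's own figure.** n = (2.15² + 2.15²)(1.96 + 0.84)² / 2.66² = 9.245 × 7.84 / 7.0756 = 10.24. The protocol prints 10; rounding up gives 11.

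**2. Power on the entered inputs.** Standard error = √(2 × 2.15² / n). Normal power = Φ(2.66/SE − 1.96). The t-test power comes from the noncentral t distribution with 2n − 2 degrees of freedom and noncentrality 2.66/SE. At n = 10, SE = 0.962, noncentrality = 2.766 and the critical t is 2.101 (18 df).

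| Completers per group | Normal formula | t-test |
|---|---|---|
| 10 | 79.0% | 74.4% |
| 11 | 82.7% | 78.8% |
| 12 | 85.8% | 82.5% |
| 14 | 90.5% | 88.3% |

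Simulating 100,000 trials at n = 10 gave 74.7%, in agreement with the t-test figure. So 80% needs 11 per group by the printed formula and 12 by t-test. The stated 90% at 14 holds by the normal formula and is 88.3% by t-test.

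**3. The drop-out sentence.** 15 × 0.70 = 10.5, so 10 or 11 per group remain. By t-test neither reaches 80%. By the normal formula 11 does and 10 does not.

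**4. With the SDs as stated.** n = (2.15² + 3.34²) × 7.84 / 7.0756 = 15.778 × 7.84 / 7.0756 = 17.48, so 18 by the normal formula. By t-test, power is 51.8% at 10, 56.1% at 11, 60.2% at 12, 78.8% at 18 and 81.1% at 19, so 19 are needed.

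**5. Second source.** With both stated SDs, the printed formula gives (1.3² + 1.2²) × 7.84 / 1.5² = 10.91, so 11. T-test power is 71.8% at 10, 76.3% at 11 and 80.1% at 12. With the control SD in both arms, as was done for the first source, the printed formula gives 2 × 1.3² × 7.84 / 1.5² = 11.78, so 12.

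**The case against.** **The normal formula is the usual approximation to a t-test.** That is so, and the SAP refers to a published protocol preprint that is not among the documents, so the exact calculation it describes cannot be checked. But the approximation is poor at 18 degrees of freedom, and rounding 10.24 down falls short of 80% even on the formula's own terms.

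**The drop-out sentence assumes losses below 30%.** Ten left from 15 is a 33% loss; at 27%, 11 remain. On that strict reading the sentence holds by the normal formula (82.7%) and misses by 1.2 points by t-test (78.8%). This stands, and it makes the shortfall in that sentence small on the entered SD.

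**A reader might infer that the protocol mixes two test bases**, a normal formula for the 10 and a t-test for the 12. The documents do not show this. Entering the control SD of 1.3 in both arms gives 11.78 by the printed formula, so one method with rounding to the nearest whole number reproduces both figures.

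**No confirmatory test compares cells of 10.** SAP 3.1 and 6.1 compare whole arms in a mixed model and enter IFNGS on a continuous scale. With 20 completers per arm, t-test power on the entered inputs is 96.8%, or 93.8% at the Bonferroni level of 0.025. This stands on those inputs. With the stated SDs the same figures are 83.1% and 74.3%. Baseline adjustment could raise them, but the documents give no correlation with which to quantify that.

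**Conclusion.** The point holds, with a limited consequence. On the plan's entered inputs, 10 completers per group do not deliver 80% power by either method: they fall 1.0 point short by the printed formula and 5.6 points short by the t-test. All the figures from 74% to 83% rest on a common SD of 2.15, which the protocol does not justify and which conflicts with its stated 3.34 for the intervention arm. That substitution matters more than rounding or the choice of distribution: with the stated SDs, t-test power at 10 is 51.8%.

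A reader might therefore conclude that both planning sources need 12 per group. That is true of the first source only if 2.15 is accepted for both arms; on its stated SDs it needs 19 by t-test. A reader might also conclude that the primary comparisons are underpowered because of the rounding. The documents do not support that, since those comparisons use whole arms. What fails is the stated basis for 40 completers as four cells with 80% power each.

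**What to change.** In SAP section 4, and in protocol 3.9.18 if it is amended:

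- Name one test and one rule for the SDs (a justified common SD, or both stated SDs), round up, and apply the same rules to both planning sources.
- Print the resulting t-test power for 10 to 11 completers per group at two-sided 0.05: about 74–79% if a common SD of 2.15 is justified, about 52–56% with 2.15 and 3.34, and about 72–76% under the second source. The 74% and the requirement of 12 should not be printed alone as the corrected figures.
- Remove the statement that 10 per group gives 80% power, and bring the 15-per-group and 14-per-group statements into line.
- Present 40 completers as a recruitment target that does not give 80% power per cell, and add that the confirmatory tests compare whole arms with IFNGS continuous.

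The cost is a rewritten sample-size paragraph and a less favourable stated power. No new patients, data or procedures are needed.

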## 3 Methods

### 3.1 Study design and study settings

The study is designed as an investigator-blinded randomized controlled trial consisting of 12 weeks of endurance exercise (Figure 1). A total of 60 patients will be randomized to intervention in a 1:1 fashion, a total of 30 patients will follow an exercise intervention, while the remaining will be encouraged to maintain current exercise habits for the duration of the study (see Figure 1).

[figure not shown]

Figure 1 Study Design

The enrolment period is planned to start in early 2022 and run for approximately two years or when 30 patients are recruited to each group. Follow-up is estimated to be completed in the spring of 2023. All baseline and follow-up tests will be carried out at Centre for Physical Activity Research (CFAS), Rigshospitalet, Denmark.  $^{82}\text{Rb}$ -PET scans will be performed at the Department of Clinical Physiology, Nuclear Medicine & PET, Rigshospitalet, Denmark. All data will be collected and analysed in Denmark.

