## 4 Ethical considerations

### 4.1 General information

This study will be conducted in accordance with Regional Ethics Committee (REC) and the Declaration of Helsinki. All participants must sign an informed consent form before enrolment. The protocol will be submitted to the Capital Regional Ethics Committee and to the Danish Data Protection Agency. Information regarding participants of the project will be protected in accordance with the applicable laws of Denmark including laws concerning the processing of personal data (“databeskyttelsesforordningen” and “databeskyttelsesloven”). Amendments and modifications to

Sample Size	
Group 1	10
Group 2	10
Total	20
Study Parameters	
Mean, group 1	1.14
Mean, group 2	3.8
Alpha	0.05
Beta	0.2
Power	0.8

the protocol will be sent to the Regional Ethics Committee and the Danish Data Protection Agency for approval and no changes to the protocol will be established before approval.

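### The sample-size formula uses the control SD (2.15) for both arms although the intervention SD is given as 3.34; on the stated SDs, 80% power needs 19 per group by t-test (18 by the protocol's formula), not 10

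*Protocol*

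**What the plan says.** Protocol 3.9.18 takes its first planning scenario from a published study: a mean VO2max change of 1.14 ml/kg/min with SD 2.15 in controls, and "3.80ml/kg/min with a SD of 3.34 in the intervention group". It asks for 80% power at a significance level of 0.05. The formula is written with distinct sigma terms for the two groups, and the substitution shown is "2.15^2 + 2.15^2/1)(1.96 + 0.84)^2", divided by 2.66 squared. The printed result is 10 per group.

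Further statements follow from that result:

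- With 15 per group, "we will have at least a power of 80% even with 30% drop-out".
- The claim for higher power reads: "With 14 participants in each group, we will achieve a power of 90" per cent.
- If a third of patients have a high IFNGS, "including 30 patients for intervention will give us 10" high-IFNGS exercisers for this calculation. This matches 3.1, where "a total of 30 patients will follow an exercise intervention".

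A table printed within 4.1 (the block headed "Study Parameters" and the rows above it) repeats 10, 10 and 20 in total at power 0.8.

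A second planning study (changes of 1.7 and 3.2, SDs 1.3 and 1.2) is treated separately: "A significance of 0.05 and a power of 80% requires 12 subjects in each group".

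SAP section 4 says the calculation was based on a t-test, repeats 10 completers per group for a difference of 2.66, and multiplies by four IFN-by-treatment cells to reach 40 completers. It reports that recruitment ceased once 40 had completed, with 55 participants included.

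**The concern.** The SD of 3.34 is quoted as a planning input and then does not appear in the calculation. Neither document gives a reason, such as an equal-variance assumption. The intervention SD is the larger of the two, so replacing it with the control SD understates the variance and the required sample.

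The resulting 10 is not an isolated figure. It supports the 30 per arm in the protocol and the 40-completer target in the SAP. If it stands, readers will take groups of about 10 to have 80% power when the protocol's own inputs do not support that.

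**Working it through.** **Inputs (protocol 3.9.18).** Difference 3.80 − 1.14 = 2.66. SDs 2.15 and 3.34. Two-sided 0.05 (z = 1.96). Power 80% (z = 0.84). Allocation 1:1.

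**Formula.** n per group = (s1² + s2²)(z_alpha + z_power)² / difference², where (1.96 + 0.84)² = 7.84 and 2.66² = 7.0756.

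**Step 1. Reproduce the plan's figures with 2.15 in both arms.**

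- 80%: (4.6225 + 4.6225) × 7.84 / 7.0756 = 10.24, printed as 10. Rounding up would give 11.
- 90% (z = 1.2816): 9.245 × 3.2416² / 7.0756 = 13.73, so 14, as printed.

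Both printed figures come from this substitution, so the slip drove the results and is not a misprint in one line.

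**Step 2. Use the stated SDs.** 2.15² + 3.34² = 4.6225 + 11.1556 = 15.7781.

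- 80%: 15.7781 × 7.84 / 7.0756 = 17.48 (17.50 with unrounded z), so 18 per group.
- 90%: 15.7781 × 3.2416² / 7.0756 = 23.43, so 24 per group.
- Two-sided t-test (noncentral t): 19 per group for 80% (18 gives 78.4%) and 25 for 90% (24 gives 89.2%).

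**Step 3. Power at the sizes the plan names**, SDs 2.15 and 3.34, two-sided 0.05:

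| Per group | Welch t-test | Normal approximation | Plan states |
|---|---|---|---|
| 10 | 51.0% | 56.3% | 80% |
| 14 | 66.9% | 70.7% | 90% |
| 15, no drop-out | 70.1% | 73.7% | – |
| 10 to 11 (15 less 30% = 10.5) | 51.0–55.4% | 56.3–60.3% | at least 80% |

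Simulation of the Welch test (200,000 trials) agrees: 50.8% at 10, 66.8% at 14 and 80.5% at 19.

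**Step 4. The two-arm VO2max comparison**, same SDs and difference, unadjusted (Welch to normal):

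| Completers per arm | Alpha 0.05 | Alpha 0.025 |
|---|---|---|
| 20 | 82.8–85.0% | 73.8–77.4% |
| 21 (30 less 30%) | 84.6–86.6% | 76.2–79.6% |
| 23 | 87.9–89.5% | 80.6–83.4% |

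**Step 5. Second planning study.** (1.3² + 1.2²) × 7.84 / 1.5² = 10.91 by the formula. A t-test needs 12 (power 80.1%), which matches the printed 12, so that figure is sound. It also shows that the two scenarios were reported on different bases: the normal formula for the first, the t-test for the second.

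**The case against.** The error cannot be explained away, but several points limit what follows from it.

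- *No planned test depends on the 10.* SAP 6.1 analyses IFNGS on a continuous scale, and the two-arm comparison keeps more than 80% power at the protocol's alpha. This stands, and it makes the matter a reporting correction.
- *Forty completers is a minimum.* The SAP let participants already enrolled continue, giving 55 in all. The final number of completers and their split by arm are not stated. With 23 per arm, power at 0.025 is already above 80%. So the 74–77% holds for exactly 20 per arm and should be labelled that way.
- *The planned model may be more efficient than a two-sample test.* It may, but neither document gives a baseline correlation, so the gain cannot be sized.
- *The second study is more favourable.* On its inputs, 10 per group has 72–76% power at 0.05. That is still below 80%, and SAP section 4 relies on the first study alone.
- *Recruitment is over and the SAP reports history.* The historical figure should remain visible as what was planned. That does not justify leaving its stated power uncorrected.

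**Conclusion.** The concern holds. On the protocol's own inputs (difference 2.66, SDs 2.15 and 3.34, two-sided 0.05), 80% power needs 19 per group by t-test or 18 by the printed formula, and 90% needs 25 or 24. The three statements resting on 2.15 in both arms (10 for 80%, 14 for 90%, 15 with 30% drop-out) are wrong, as are the table in 4.1 and the use of 10 in SAP section 4 as a per-group requirement.

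The practical effect is moderate. The per-cell power is overstated, but it is not the power of any planned test. The overall comparison falls below 80% only at the Bonferroni level of 0.025, which SAP 6.2 added and discloses, and only if completers are near the minimum of 20 per arm. All of this concerns VO2max. It says nothing about power for the FSS co-primary endpoint, for which neither document gives a calculation.

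**What to change.** Changes to text only:

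1. **Protocol 3.9.18, formula.** Replace the substitution with (2.15² + 3.34²), label the result (17.5) as a normal approximation, and state the requirement by one named method. By t-test this is 19 per group for 80% and 25 for 90%, on the same basis as the 12 for the second study, which stays as a separate scenario.
2. **Protocol 3.9.18 and the table in 4.1.** Withdraw the claims of 10 per group for 80%, 14 for 90%, and 15 holding 80% after 30% drop-out. Change the table to 19, 19 and 38. Reword the sentence on 10 high-IFNGS exercisers so that it no longer implies adequate power.
3. **SAP section 4, per-cell power.** Add: *On the SDs given in protocol 3.9.18 for VO2max change (2.15 and 3.34, difference 2.66), 10 completers per cell gives about 51–56% power at two-sided 0.05, not 80%. This four-cell figure is not the power of the planned continuous-IFNGS interaction test.*
4. **SAP section 4, two-arm power.** Add: *On the same inputs, the two-arm VO2max comparison with 20 completers per arm, the minimum under an equal split, has about 83–85% power at 0.05 and about 74–77% at the Bonferroni level of 0.025. These are unadjusted two-sample calculations (Welch t-test to normal approximation) and exclude any precision gain from the baseline-constrained mixed model, for which no correlation was specified.*

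The original figures can be kept as a dated record of what was planned. The cost is redrafting, plus the approval step that protocol 4.1 requires for protocol changes. The estimand, model, alpha, analysis sets and number of patients do not change.
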